17.2 Serious Adverse Event (SAE) Reporting

An adverse event is considered serious if it results in ANY of the following outcomes:

- Death
- A life-threatening adverse event
- An adverse event that results in inpatient hospitalization or prolongation of existing hospitalization
- A persistent or significant incapacity or substantial disruption of the ability to conduct normal life functions
- A congenital anomaly/birth defect
- Important Medical Events (IME) that may not result in death, be life threatening, or require hospitalization may be considered serious when, based upon medical judgment, they may jeopardize the patient or subject and may require medical or surgical intervention to prevent one of the outcomes listed in this definition

Note: Hospital admission for a planned procedure/disease treatment is not considered an SAE.

SAE reporting is required as soon as the participant signs consent. SAE reporting is required for 30-days after the participant's last investigational treatment or intervention. Any events that occur after the 30-day period and that are at least possibly related to protocol treatment must be reported.

If an SAE requires submission to the IRB office per IRB SOP RR-408 'Reporting of Serious Adverse Events', the SAE report must be sent to the IRB within 5 calendar days of the event. The IRB requires a Clinical Research Database (CRDB) SAE report be submitted electronically to the SAE Office as follows:

For IND/IDE trials: Reports that include a Grade 5 SAE should be sent to [contact]. All other reports should be sent to [contact].

For all other trials: Reports that include a Grade 5 SAE should be sent to [contact]. All other reports should be sent to [contact].

The report should contain the following information:

Fields populated from CRDB:

- Subject's initials
- Medical record number
- Disease/histology (if applicable)

- Protocol number and title

Data needing to be entered:

- The date the adverse event occurred
- The adverse event
- The grade of the event
- Relationship of the adverse event to the treatment (drug, device, or intervention)
- If the AE was expected
- The severity of the AE
- The intervention
- Detailed text that includes the following
 - A explanation of how the AE was handled
 - A description of the subject's condition
 - Indication if the subject remains on the study
- If an amendment will need to be made to the protocol and/or consent form
- If the SAE is an Unanticipated Problem

The PI's signature and the date it was signed are required on the completed report.

For IND/IDE protocols:

The CRDB SAE report should be completed as per above instructions. If appropriate, the report will be forwarded to the FDA by the SAE staff through the IND Office

17.2.1 Additional Information on Serious Adverse Event (SAE) Reporting

Collection of Safety Information

An Adverse Event (AE) is defined as any new untoward medical occurrence or worsening of a pre-existing medical condition in a patient or clinical investigation subject administered an investigational (medicinal) product and that does not necessarily have a causal relationship with this treatment. An AE can therefore be any unfavorable and unintended sign (including an abnormal laboratory finding, for example), symptom, or disease temporally associated with the use of investigational product, whether or not considered related to the investigational product.

Although overdose and cancer are not always serious by regulatory definition, these events should be reported on an SAE form and sent to BMS in an expedited manner. An overdose is defined as the accidental or intentional ingestion or infusion of any dose of a product that is considered both excessive and medically important.

Note that all pregnancies, regardless of outcome, must be reported to the sponsor on a Pregnancy Surveillance Form, not an SAE form. All pregnancies must be reported and followed to outcome, including pregnancies that occur in the female partner of a male study subject. See Section 8.4 for instructions on reporting pregnancies.

Nonserious Adverse Events

All adverse events that are not classified as serious.

Assignment of Adverse Event Intensity and Relationship to Investigational Product

All adverse events, including those that are serious, will be graded according to the National Cancer Institute Common Toxicity Criteria for Adverse Events (NCI CTCAE), Version 4.0.

The following categories and definitions of causal relationship to investigational product as determined by a physician should be used for adverse events:

- Definite: The AE is clearly related to the intervention.
- Probable: The AE is likely related to the intervention.
- Possible: The AE may be related to the intervention.
- Unlikely: The AE is doubtfully related to the intervention.
- Unrelated: The AE is clearly NOT related to the intervention.

Collection and Reporting

Adverse events can be spontaneously reported or elicited during open-ended questioning, examination, or evaluation of a subject. (In order to prevent reporting bias, subjects should not be questioned regarding the specific occurrence of one or more AEs.)

If known, the diagnosis of the underlying illness or disorder should be recorded, rather than its individual symptoms. The following information should be captured for all AEs: onset, duration, intensity, seriousness, relationship to investigational product, action taken, and treatment required. If treatment for the AE was administered, it should be recorded in the medical record.

The investigator shall supply the sponsor and Ethics Committee with any additional requested information, notably for reported deaths of subjects.

Collection and Reporting for Serious Adverse Events

The investigator should notify BMS of any SAE occurring after the previously specified time period that is believed to be certainly, probably, or possibly related to the investigational product or protocol-specified procedure.

All SAEs whether related or unrelated to the ipilimumab, must be immediately reported to BMS Worldwide Safety (by the investigator or designee) within 24 hours of becoming aware of the event. If only limited information is initially available, follow-up reports are required. The original SAE form must be kept on file at the study site.

All SAEs should be faxed or emailed to BMS at:

Memorial Sloan Kettering Cancer Center
IRB Protocol #: 16-495 A(5)
Approved: 3-MAY-2017

Global Pharmacovigilance & Epidemiology
Bristol-Myers Squibb Company
[contact]
Email: [contact]

For studies conducted under an Investigator IND, any event that is both serious and unexpected must be reported to the FDA as soon as possible and, in no event, later than 7 days (death or life-threatening event) or 15 days (all other SAEs) after the investigator's or institution's initial receipt of the information. BMS will be provided with a simultaneous copy of all adverse events filed with the FDA. SAEs should be reported on the MedWatch Form 3500A, which can be accessed at:

<http://www.accessdata.fda.gov/scripts/medwatch/>.

MedWatch SAE forms should be sent to the FDA at:

MEDWATCH
[name]
[name]
Fax: [name] ([name])
<http://www.accessdata.fda.gov/scripts/medwatch/>

All SAEs should simultaneously be faxed or e-mailed to BMS at:

Global Pharmacovigilance & Epidemiology
Bristol-Myers Squibb Company
[contact]
Email: [contact]

Serious adverse events, whether related or unrelated to investigational product, must be recorded on the SAE page and reported expeditiously to BMS (or designee) to comply with regulatory requirements. An SAE report should be completed for any event where doubt exists regarding its status of seriousness.

All SAEs must be immediately reported by confirmed facsimile transmission (fax) and mailing of the completed SAE page. In some instances where a facsimile machine is not available, overnight express mail may be used. If only limited information is initially available, follow-up reports are required. (Note: Follow-up SAE reports should include the same investigator term(s) initially reported.) In selected circumstances, the protocol may specify conditions that require additional telephone reporting.

If the investigator believes that an SAE is not related to the investigational product, but is potentially related to the conditions of the study (such as withdrawal of previous therapy, or a complication of a study procedure), the relationship should be specified in the narrative section of the SAE page.

If an ongoing SAE changes in its intensity or relationship to the investigational product, a follow-up SAE report should be sent immediately to the sponsor. As follow-up information becomes available it should be sent immediately using the same procedure used for transmitting the initial SAE report. All SAEs should be followed to resolution or stabilization.

Handling of Expedited Safety Reports

In accordance with local regulations, BMS will notify investigators of all SAEs that are suspected (certainly, probably, or possibly related to the investigational product) and unexpected (i.e., not previously described in the Investigator Brochure). In the European Union (EU), an event meeting these criteria is termed a Suspected, Unexpected Serious Adverse Reaction (SUSAR). investigator notification of these events will be in the form of an expedited safety report (ESR).

Other important findings which may be reported by the sponsor as an ESR include: increased frequency of a clinically significant expected SAE, an SAE considered associated with study procedures that could modify the conduct of the study, lack of efficacy that poses significant hazard to study subjects, clinically significant safety finding from a nonclinical (eg, animal) study, important safety recommendations from a study data monitoring committee, or sponsor decision to end or temporarily halt a clinical study for safety reasons.

Upon receiving an ESR from BMS, the investigator must review and retain the ESR with the Investigator Brochure. Where required by local regulations or when there is a central IRB/IEC for the study, the sponsor will submit the ESR to the appropriate IRB/IEC. The investigator and IRB/IEC will determine if the informed consent requires revision. The investigator should also comply with the IRB/IEC procedures for reporting any other safety information.

In addition, suspected serious adverse reactions (whether expected or unexpected) shall be reported by BMS to the relevant competent health authorities in all concerned countries according to local regulations (either as expedited and/or in aggregate reports).

Nonserious Adverse Events

The collection of nonserious AE information should begin at initiation of investigational product. Nonserious AE information should also be collected from the start of a placebo lead-in period or other observational period intended to establish a baseline status for the subjects.

If an ongoing nonserious AE worsens in its intensity, or if its relationship to the investigational product changes, a new nonserious AE entry for the event should be completed. Nonserious AEs should be followed to resolution or stabilization, or reported as SAEs if they become serious. Follow-up is also required for nonserious AEs that cause interruption or discontinuation of investigational product, or those that are present at the end of study participation. Subjects with nonserious AEs at study completion should receive post-treatment follow-up as appropriate.

All identified nonserious AEs must be recorded and described in the medical record.

Pregnancy

Sexually active WOCBP must use an effective method of birth control during the course of the study, in a manner such that risk of failure is minimized. Before enrolling WOCBP in this clinical study, the investigator must review the guideline about study participation for WOCBP which can be found in the GCP Manual for Investigators. The topics include the following:

- General Information
- Informed Consent Form
- Pregnancy Prevention Information Sheet
- Drug Interactions with Hormonal Contraceptives
- Contraceptives in Current Use
- Guidelines for the Follow-up of a Reported Pregnancy.

Before study enrollment, WOCBP must be advised of the importance of avoiding pregnancy during study participation and the potential risk factors for an unintentional pregnancy. The subject must sign an informed consent form documenting this discussion.

All WOCBP MUST have a negative pregnancy test within 72 hours before receiving ipilimumab. The minimum sensitivity of the pregnancy test must be 25 IU/L or equivalent units of HCG. If the pregnancy test is positive, the subject must not receive ipilimumab and must not be enrolled in the study.

In addition, all WOCBP should be instructed to contact the investigator immediately if they suspect they might be pregnant (e.g., missed or late menstrual period) at any time during study participation.

If, following initiation of the investigational product, it is subsequently discovered that a study subject is pregnant or may have been pregnant at the time of investigational product exposure, including during at least 6 half-lives after product administration, the investigational product will be permanently discontinued in an appropriate manner (eg, dose tapering if necessary for subject safety). The investigator must immediately notify BMS of this event and record the pregnancy on the Pregnancy Surveillance Form (not an SAE form). Initial information on a pregnancy must be reported immediately to BMS, and the outcome information provided once the outcome is known. Completed Pregnancy Surveillance Forms must be forwarded to BMS according to SAE reporting procedures.

Any pregnancy that occurs in a female partner of a male study participant should be reported to the sponsor. Information on this pregnancy will be collected on the Pregnancy Surveillance Form.

Protocol-required procedures for study discontinuation and follow-up must be performed on the subject unless contraindicated by pregnancy (e.g., x-ray studies). Other appropriate pregnancy

follow-up procedures should be considered if indicated. In addition, the investigator must report to BMS, and follow-up on information regarding the course of the pregnancy, including perinatal and neonatal outcome. Infants should be followed for a minimum of 8 weeks.

Other Safety Considerations

Any significant worsening noted during interim or final physical examinations, electrocardiograms, x-rays, and any other potential safety assessments, whether or not these procedures are required by the protocol, should also be recorded in the medical record.

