6.1 Subject Inclusion Criteria

Subjects must meet the following criteria at screening to be eligible to participate in the study.

- Women age 18 years or older
- Confirmed histologic diagnosis of invasive adenocarcinoma of the breast, including MSKCC pathology confirmation
- ER, PR and HER2 testing in progress (i.e. on outside or MSKCC biopsy report)
 - HER2-positive pathology is permitted
- Operable tumor measuring ≥ 1.5 cm in maximal diameter
 - Any nodal status
 - Multifocal and multicentric disease is permitted.
 - Synchronous bilateral invasive breast cancer is permitted
 - The tumor should be more than 5 mm from the skin.
- No indication of distant metastases
- Breast surgery planned
- Tumor amenable to cryoablation as determined by radiologist
- ECOG performance status score of 0 or 1.
- Screening laboratory values must meet the following criteria:
 - i. White blood cells (WBCs) $\geq 2000/\mu\text{L}$
 - ii. Absolute neutrophil count (ANC) $\geq 1500/\mu\text{L}$
 - iii. Platelets $\geq 100 \times 10^3/\mu\text{L}$
 - iv. Hemoglobin $\geq 11.0 \text{ g/dL}$
 - v. Serum creatinine $\leq 2 \text{ mg/dL}$ (or glomerular filtration rate $\geq 40 \text{ ml/min}$)
 - vi. AST $\leq 2.5 \times$ upper limit of normal (ULN)
 - vii. ALT $\leq 2.5 \times$ ULN
 - viii. Bilirubin within normal limits (except subjects with Gilbert's syndrome, who must have total bilirubin $< 3.0 \text{ mg/dL}$)
 - ix. Negative HIV screening test
 - x. Negative screening tests for Hepatitis B and Hepatitis C.

Patients with positive results that do not indicate true active or chronic infection may enroll after discussion and consensus agreement by the treating physician and principal investigator.
- Women of childbearing potential (WOCBP) must be using an acceptable method of contraception to avoid pregnancy throughout the study and for at least 3 months after the last dose of ipilimumab in such a manner that the risk of pregnancy is minimized. See below for the definition of WOCBP.
- WOCBP must have a negative serum pregnancy test within 14 days prior to the first dose of ipilimumab/nivolumab.
- Women must not be breastfeeding.

- Willing to adhere to the study visit schedule and the prohibitions and restrictions specified in this protocol.

Definition of WOCBP

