Ipilimumab is to be administered as an IV infusion with a 0.2 μ m or 1.2 μ m in-line filter using a volumetric pump, at the 1 mg/kg dose, to complete the infusion in 90 minutes with at least 10 cc normal saline flush at the end. The total dose needed should be prepared and administered per institutional guidelines. The total dose must be calculated using the most recent subject weight (obtained on the same day of, and prior to, the infusion).

Nivolumab is to be administered as an IV infusion with a 0.2 μ m or 1.2 μ m in-line filter using a volumetric pump, at the 3 mg/kg dose, to complete the infusion in 60 minutes with at least 10 cc normal saline flush at the end. The total dose needed should be prepared and administered per institutional guidelines. The total dose must be calculated using the most recent subject weight (obtained on the same day of, and prior to, the infusion).

Separate infusion bags and filters must be used for each infusion. Nivolumab is to be administered first. The nivolumab infusion must be promptly followed by a saline flush to clear the line of nivolumab before starting the ipilimumab infusion.

9.2 Pre-cryoablation core biopsies:

At least three 18G MRI or US-guided core breast biopsies will be obtained at the core biopsy appointment for all participants, if feasible. If not all three core biopsies can be performed, this will not make the patient ineligible. Core biopsies of clinically or radiographically suspicious lymph nodes will also be obtained as indicated. Two core breast specimens will be provided to the MSKCC BAIC pathology department for routine (standard of care) testing. Additional core biopsy specimens will be sent to the IMF for research purposes as detailed in section 12. The MRI or US-guided biopsies will be performed by investigators from the Breast Radiology Service with the assistance of investigators from Interventional Radiology and Anesthesiology as needed.

9.3 Cryoablation:

Percutaneous, MRI or US-guided cryoablation will be performed with a multiple freeze-thaw cycle. Freeze-thaw cycle strategies will be individualized to the patient and their tumor. Generally two cycles will be performed with each cycle being approximately 10 minutes of freeze time. Intermittent imaging will guide the procedure to ensure the ice ball does not encroach on critical structures, including skin. The number of probes used will depend on the lesion size and location.

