15.0 RESEARCH PARTICIPANT REGISTRATION AND RANDOMIZATION PROCEDURES

15.1 Research Participant Registration

Confirm eligibility as defined in the section entitled Criteria for Patient/Subject Eligibility.

Obtain informed consent, by following procedures defined in section entitled Informed Consent Procedures.

During the registration process registering individuals will be required to complete a protocol specific Eligibility Checklist.

All participants must be registered through the Protocol Participant Registration (PPR) Office at Memorial Sloan Kettering Cancer Center. PPR is available Monday through Friday from 8:30am – 5:30pm at [contact]. Registrations must be submitted via the PPR Electronic Registration System (<http://ppr/>). The completed signature page of the written consent/RA or verbal script/RA, a completed Eligibility Checklist and other relevant documents must be uploaded via the PPR Electronic Registration System.

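### Section 6.1 accepts a pregnancy test up to 14 days old at dosing, Section 17.2.1 demands one within 72 hours before ipilimumab, and no visit schedule lists the test

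*Combined protocol and SAP*

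**What the plan says.** Two sections set a time limit for the same pre-dose check.

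- Section 6.1 (inclusion criteria): "WOCBP must have a negative serum pregnancy test within 14 days prior to the first dose of ipilimumab/nivolumab". Contraception is a separate criterion: "Women of childbearing potential (WOCBP) must be using an acceptable method of contraception to avoid pregnancy throughout the study".
- Section 17.2.1, under Pregnancy: "All WOCBP MUST have a negative pregnancy test within 72 hours before receiving ipilimumab". It adds a performance floor, "The minimum sensitivity of the pregnancy test must be 25 IU/L or equivalent units of HCG", and a consequence, "If the pregnancy test is positive, the subject must not receive ipilimumab and must not be enrolled in the study".

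Three other places bear on how these rules reach the clinic.

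- Section 15.1 tells the registering staff: "Confirm eligibility as defined in the section entitled Criteria for Patient/Subject Eligibility". That is Section 6, which carries the 14-day window.
- Section 8.0 itemises the baseline bloods (chemistry, blood count, thyroid and other hormones including FSH/LH, HIV and hepatitis screens, research tubes) and the other screening assessments (history, examination, performance status, ECG). No pregnancy test is among them. Appendix 1 has no row for one, and its footnote naming the baseline bloods omits it too.
- Section 9.1.2, on the order of the two infusions: "Nivolumab is to be administered first". Nivolumab runs for 60 minutes and the line is flushed before ipilimumab starts.

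**The concern.** The stricter rule sits in a section on serious adverse event reporting, while the sections that staff use to register, screen and schedule a patient either carry the looser rule or do not mention the test. Nothing in Section 6.1, 8.0 or Appendix 1 refers the reader to the 72-hour requirement. Section 8.0 also ties the baseline bloods to presurgical testing within 14 days of dosing. If the pregnancy test is drawn with them, which is the natural arrangement, it can be older than 72 hours when the drugs are given.

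What is at stake is patient safety and protocol compliance. Both drugs are given once. If pregnancy is discovered after dosing, the response in Section 17.2.1 is that "the investigational product will be permanently discontinued in an appropriate manner", which cannot reverse a single dose already infused.

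The drug wording adds a smaller gap. Section 17.2.1 times the test to ipilimumab and bars only ipilimumab after a positive result. Taken literally, it does not stop the nivolumab infusion that comes first.

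**Working it through.** The plan gives no figure to reproduce. The check sets the rules side by side, with simple arithmetic on the windows.

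1. **Windows.** Section 6.1: 14 days × 24 = 336 hours before the first dose of either drug. Section 17.2.1: 72 hours, or 72 / 24 = 3 days, before ipilimumab.
2. **Difference.** 336 − 72 = 264 hours; 264 / 24 = 11 days. A test taken more than 3 and up to 14 days before dosing passes Section 6.1 and fails Section 17.2.1. (This ignores the short offset between the two infusions, taken up in step 5.)
3. **Can both be met?** Yes. A negative serum test of the required sensitivity, taken within 72 hours and before the infusions, satisfies both sections.
4. **Which rule would staff meet?**
   - Registration (Section 15.1) points to Section 6: 14 days.
   - Pretreatment lists (Section 8.0): no pregnancy test.
   - Timetable and footnote (Appendix 1): no pregnancy test.
   - Pregnancy text (Section 17.2.1): 72 hours.

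   Only the last of these carries the rule that governs dosing.
5. **Drug named.** Section 6.1 refers to both drugs; Section 17.2.1 refers to ipilimumab only. Nivolumab takes 60 minutes and goes first, so it starts at least 1 hour before the event to which Section 17.2.1 ties the test. A result first read between the two infusions would meet that section's wording after nivolumab had been given.
6. **Patients affected.** Only women of childbearing potential. The documents give no expected share, so the range is 0 to 6 of the 6 patients.
7. **Effect on the analysis.** The primary endpoint in Section 14.0 counts patients without a grade 3 or 4 adverse event that delays surgery. The requirement of 5 or 6 out of 6, and the stated probabilities of 0.53, 0.65 and 0.89, do not depend on the timing of the pregnancy test.

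**The case against.** The best reply is that the rules are cumulative. Section 6.1 sets eligibility and Section 17.2.1 sets a mandatory condition for dosing. Meeting the first does not waive the second, so dosing on a ten-day-old test would be a deviation, not something the protocol allows. This stands. A reader might infer that the two rules contradict each other, or that the protocol authorises dosing on an old test; the text supports neither. What remains is that the binding rule is absent from the places where staff would look for it.

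Other safeguards exist. Contraception is required, Appendix 1 schedules a history and physical examination on the dosing day, women are told to report a suspected pregnancy at once, and Section 13.0 already makes pregnancy a ground for removal. These lower the chance of harm, but a history does not replace the test.

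A reader might also infer that a woman could receive nivolumab without any test. She could not if Section 6.1 is followed, because its criterion covers both drugs. The gap is confined to an earlier negative test followed by a later positive one, where Section 17.2.1 withholds only ipilimumab by name.

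Appendix 1 is a summary grid, and it has no row for the cryoablation procedure either, so its silence alone is weak evidence. The omission from the itemised lists in Section 8.0 and in the Appendix 1 footnote carries more weight. Finally, the Eligibility Checklist mentioned in Section 15.1 is not in the documents and may already contain the 72-hour rule.

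**Conclusion.** The point holds as a mismatch between stated safety rules that should be aligned. It is minor, and it has no bearing on the trial's conclusions. Section 17.2.1 excludes 11 of the 14 days that Section 6.1 allows. That ratio describes the windows and is not an estimate of the risk of exposure in pregnancy, for which the documents give no basis.

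The practical consequence, dosing on a test older than 72 hours, assumes a site that works from Section 6.1, Section 8.0 and Appendix 1 and a checklist that does not carry the stricter rule. The second assumption cannot be verified. The ipilimumab-only wording is a real but narrow gap and is closed by the same edit.

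**What to change.** State one rule in both Section 6.1 and Section 17.2.1, for example: *negative serum pregnancy test (minimum sensitivity 25 IU/L HCG) within 72 hours before the first infusion (nivolumab); if positive, neither nivolumab nor ipilimumab is given.* Add the test to the Section 8.0 list and as a row at Visit 4 in Appendix 1, with the result reviewed before nivolumab starts.

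This keeps the sponsor's own stricter window and moves it to where staff will see it. The cost is wording in three sections, one timetable row, and at most one test per woman of childbearing potential (0 to 6 tests), which Section 17.2.1 already requires. Sample size, dosing and surgery dates do not change. One practical detail needs settling: a woman registered more than 72 hours before dosing will still have this criterion open, so the checklist should let it be closed at Visit 4, before any drug is given.
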